1.0 STUDY OBJECTIVES

1.1 Primary Objective:

To assess the efficacy of administering Early Metabolic Resuscitation with Standard of Care (SC + EMR) in patients diagnosed with septic shock for reducing 28-day mortality versus using the Standard of Care alone (SC). Twenty-eight day mortality is defined during the time from the day SC+EMR or SC was first administered until a patient dies or is followed through 28 days (whichever comes first).

1.2 Secondary Objectives:

1. To assess whether Early Metabolic Resuscitation with standard of care (SC + EMR) is an effective strategy to reduce ICU mortality, hospital mortality, and 90-day mortality of septic shock patients relative to SC. ICU mortality is defined as mortality at ICU discharge relative to SC.
2. To compare the time to death from any cause between patients administered SC + EMR versus SC after being diagnosed with septic shock.
3. To assess whether SC + EMR is an effective strategy to reduce complications of septic shock such as: i) acute kidney injury, ii) dialysis requirements, iii) need for cardiovascular support or days on vasopressors, iv) need for invasive ventilation, days on ventilator support, v) duration of ICU stay, and vi) duration of hospital stay versus SC.
4. To describe the presence of any adverse effects between the two study groups (SC + EMR group vs SC group); thus, characterizing their safety.

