 - a. Time from hospital admission to admission to the ICU (Length of stay before admission to the ICU)
 - b. Length of the stay in the ICU
 - c. Length of hospital stay
- 2. Mortality
 - a. Hospital mortality
 - b. ICU mortality
 - c. 28 day mortality
 - d. 90 day mortality
- 3. Ventilator days – ventilator free days, duration of intubation (days)
- 4. Any newly documented hospital acquired infection(s)
- 5. Any acute kidney injury as defined by acute kidney injury network criteria:
 - a. An acute (within 48h) rise in serum creatinine of 0.3g/dl or more

- b. A percentage increase of serum creatinine of 50% or more
 - c. Documented oliguria <0.5 ml/kg/hr for >6 hours
 - d. Need for dialysis
 - e. Dialysis free days
- 6. Inotropic free days and duration of inotropic support (hours or days)
- 7. Vital signs and any hemodynamic monitoring (cardiac index, CVP, ScvO2) implemented will be recorded – there is no specific requirement for hemodynamic monitoring beyond arterial-line recorded MAP/BP/HR.
- 8. All patients will be followed up for up to 90 days.

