10.0 STATISTICAL CONSIDERATIONS

10.1 Study Endpoint and Outcomes

The primary objective of this study is to assess the efficacy of administering Early Metabolic Resuscitation with Standard of Care (SC + EMR) in patients diagnosed with septic shock for reducing 28 day mortality versus using the Standard of Care alone (SC).

The primary endpoint of the study is 28-day mortality. The rationale for selecting the 28-day timeframe as the primary endpoint for comparison is that the MDACC ICU length of stay and the hospital length of stay in patients diagnosed with septic shock have wide variability (ICU LOS = Mean 9.45 ± 13.06 min: 0 max: 104, and Hospital LOS = Mean $26.4 \pm SD 26.4$ min:1, max: 242). This variability is incurred from sources that cannot be controlled. For this reason, measures such as 28-day and 90-day mortality provide more objectivity and align with outcomes described in the literature.

Secondary outcomes include ICU mortality, hospital mortality, 90-day mortality, incidence of acute kidney injury (dichotomous variable), time on cardiovascular support (continuous variable), time on ventilator (continuous variable) and length of ICU and hospital stays (continuous variables).

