10.5 Data Analyses

Descriptive statistics including the mean, standard deviation, median, and range will be used to summarize continuous variables. Frequency counts and percentages will be used to summarize categorical variables. Categorical variables, including 28 day mortality, will be compared between intervention groups using a chi-square test, or Fisher's exact tests if more appropriate. Continuous variables will be compared between intervention groups using an independent samples t-test, or Wilcoxon rank-sum test if more appropriate.

Logistic regression will be used to assess relationships between patient characteristics and binary study outcomes of interest. Continuous variables, including the time on cardiovascular support and time on ventilator, will be compared using t-tests or Wilcoxon rank-sum tests.

Time to event analyses will be conducted using Cox proportional hazards regression. For 28-day mortality, living patients will be censored after one month after the treatment was given. For overall survival, patients will be followed until time of death or date of last follow-up (maximum 6 months). Kaplan-Meier plots will be used to visually compare time to death from any cause between intervention arms followed by a log-rank test to compare survival distributions.

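### Ventilator, vasopressor and length-of-stay comparisons have no rule for deaths, so if mortality differs between arms a longer or shorter time cannot be read as an effect on duration

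*Combined protocol and SAP*

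**What the plan says.** Secondary objective 3 (section 1.2) asks whether EMR reduces complications, among them "need for cardiovascular support or days on vasopressors, iv) need for invasive ventilation, days on ventilator support, v) duration of ICU stay" and hospital stay. Section 10.1 lists time on cardiovascular support, "time on ventilator (continuous variable) and length of ICU and hospital stays (continuous variables") as secondary outcomes. Section 10.5 then says "Continuous variables, including the time on cardiovascular support and time on ventilator, will be compared using t-tests or Wilcoxon rank-sum tests". ICU and hospital stay fall under that section's general sentence on continuous variables, which names the same tests.

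The censoring and follow-up rules in section 10.5 concern death only (28-day mortality and overall survival). Nothing there, or elsewhere, says what duration is assigned to a patient who dies on a ventilator, on vasopressors, in the ICU or in hospital.

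The outcome data in section 7.2 do include "ventilator free days, duration of intubation (days") and "Inotropic free days and duration of inotropic support (hours or days"). Neither free-day item has a window or a score for death, and section 10 names neither as an analysed outcome. No ICU-free or hospital-free days are listed.

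**The concern.** If the recorded duration simply stops at death, a patient who dies on day 2 contributes a short value, and under objective 3 a short value is favourable. That matters little when deaths are few or equal between arms. Here the trial is designed around a large mortality difference, with over half the patients expected to die by day 28.

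The difference between arms in raw duration is still a valid randomised comparison of a recorded quantity. What fails is the interpretation: it responds to who died as well as to how long support was needed, and the two cannot be separated afterwards. An effective treatment could appear to prolong support, and a harmful one could appear to shorten it.

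**Working it through.** **Inputs from the documents.** Section 10.2: 56 per arm, 1:1, 28-day mortality 70% versus 40%, two-sided 0.05, 90% power. Section 10.1: ICU stay SD 13.06 days, hospital stay SD 26.4 days. Durations by vital status are not given, so they are assumed below.

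**Plan's own figure.** Two-proportion test, pooled variance, no continuity correction, 0.70 versus 0.40, n = 56 per arm: power 90.2%. The stated 90% reproduces.

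**Share of deaths.** (0.70 + 0.40)/2 = 0.55, or 0.55 × 112 ≈ 62 patients.

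**Mechanism.** Let p be an arm's mortality, and m_D and m_S the mean durations in deaths and survivors, equal in both arms (no duration effect). The arm mean is p·m_D + (1 − p)·m_S, so

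EMR − SC = (p_SC − p_EMR) × (m_S − m_D).

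This is zero if mortality is equal or if m_S = m_D. Otherwise its sign depends on both factors.

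**Simulation for ventilator or vasopressor time.** 4,000 trials per row, 56 per arm, Monte Carlo error at most 0.8 points. Assumptions: exponential durations for deaths, lognormal for survivors (log-SD 0.6), both capped at 28 days; all patients supported; every death ends support. With medians 3 and 7 the uncapped means are 3/ln 2 = 4.33 and 7·exp(0.6²/2) = 8.38 days. The expected shift at 70% versus 40% is therefore 0.30 × 4.05 ≈ 1.2 days.

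| Mortality EMR / SC | Medians, deaths / survivors | EMR significantly longer (Wilcoxon / t) | EMR significantly shorter (Wilcoxon / t) |
|---|---|---|---|
| 40% / 70% | 3 / 7 | 32.1% / 23.9% | under 1% |
| 70% / 40% | 3 / 7 | under 1% | 32.1% / 24.9% |
| 45% / 60% | 3 / 7 | 10.6% / 8.5% | under 1% |
| 55% / 70% | 3 / 7 | 10.9% / 9.6% | under 1% |
| 40% / 70% | 7 / 7 | 2.9% / 1.5% | 1.7% / 4.2% |
| 40% / 70% | 10 / 5 | under 1% | 16.5% / 23.9% |
| 55% / 55% | 3 / 7 | 2–3% | 2–3% |

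The 7/7 row is not exactly null because equal medians here are not equal means.

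Two relaxations of the first row: if only half of deaths cut support short (the rest having survivor-like durations), it becomes 10.7% / 9.0%; if only 60% of patients are ventilated, 7.3% / 11.9%.

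**Length of stay, normal approximation.** ICU: SE = 13.06 × √(2/56) = 2.47 days. If survivors stay an assumed 5 or 10 days longer than decedents, a 30-point mortality effect shifts the mean by 1.5 or 3.0 days, and EMR is significantly longer in 8.8% or 22.8% of trials. With a 15-point effect (0.75 or 1.5 days) the figures are 4.9% and 8.8%. Hospital: SE = 26.4 × √(2/56) = 4.99 days; a 10-day gap gives 8.7% (30 points) or 4.9% (15 points). If decedents stay longer, the sign reverses.

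**The case against.** **A reader might infer that the plan is set up to produce a false claim of benefit.** It is not. If EMR lowers mortality and survivors need support longer than those who die, the raw test works against EMR; a spurious shorter result then occurs in under 1% of trials. It arises materially only if EMR raises mortality, in which case the primary endpoint would show the deaths alongside, or if those who die have the longer support.

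**A reader might also infer an inflated type I error or a damaged primary analysis.** Neither follows. With equal mortality each tail stays at 2–3%, and the 28-day mortality test does not use these variables.

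**The size is assumed.** This stands. The 32% needs a full 30-point effect, every patient supported and every death ending support; relaxing any one of these brings it to roughly 7–12%. The 70% itself comes from 305 ICU septic-shock patients (section 2.2), whereas the trial excludes SOFA above 12.

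**Stays beyond follow-up might seem an equal problem.** Section 7.2 says "All patients will be followed up for up to 90 days", section 10.5 refers to "date of last follow-up (maximum 6 months"), and the site's maxima are 104 ICU days ("ICU LOS = Mean 9.45 ± 13.06 min: 0 max: 104") and 242 hospital days. But lognormal or gamma shapes fitted to the stated means and SDs put only about 3% of hospital stays and 0.2–0.4% of ICU stays beyond day 90. This is a side note.

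**Free days are already collected.** True, but they are undefined and unconnected to any analysis.

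**Any replacement will largely repeat the mortality comparison.** This also stands. It limits what the new outcomes can claim, but it does not justify scoring an early death as a favourable result.

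**Conclusion.** The point holds for deaths. Followed as written, sections 10.1 and 10.5 compare raw durations with no rule for patients who die, and objective 3 reads a shorter time as benefit. If mortality differs, the result cannot be interpreted as an effect on duration. Under the 3/7-day assumptions the misleading result occurs in about 32% (Wilcoxon) or 24% (t-test) of trials at 70% versus 40%, with EMR longer if it saves lives and shorter if it costs them. It falls to about 10% with a 15-point effect, is small when deaths and survivors have similar durations, reverses when deaths have the longer support, and vanishes when mortality is equal. The missing rule is certain; the size and direction of its effect cannot be derived from the documents. Only secondary outcomes are affected, so the plan should be changed, but the primary conclusion does not depend on it.

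**What to change.** In sections 10.1 and 10.5, replace the raw-duration tests:

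- **Ventilator and vasopressor/inotrope support.** Test the free-day items already in section 7.2, defined as days alive and free of support to day 28 from first study treatment. Score death by day 28 as 0 and never-supported survivors as 28. Include all randomised patients and compare by Wilcoxon rank-sum.
- **ICU and hospital stay.** Analyse time to discharge alive to day 90 with death as a competing event, using cumulative incidence and Gray's test. Name the test: a Cox model that censors deaths answers a different question. In the simulated support setting, with no duration effect at 70% versus 40%, a cause-specific log-rank test favoured EMR in anywhere from 16% to 82% of trials depending on the assumed durations.
- **Raw durations.** Report them descriptively by arm and vital status, beside mortality.
- **Interpretation.** State in advance that a significant result on either new outcome is a composite with mortality and is not by itself evidence of shorter support or stay.

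The cost is mainly drafting; the sample size does not change. Support and vital status must be collected through the window, including for patients moved to Comfort Care, whom section 6.4 removes from the study, and section 7.2 collects data only where available. The real downside is that no replacement isolates duration: with no duration effect at 70% versus 40%, free days favour EMR in about 85% of simulated trials, against about 90% for the mortality test itself. The gain is that a death is never counted as an early favourable ending, and the reader knows which way mortality pulls the result.

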10.6 Safety monitoring for Patients assigned to (SC + EMR)

Patient safety will be monitored group sequentially for the first 50 patients in (SC + EMR) group. The monitoring rule will be applied in cohorts of size 10 during the 7 days of treatment.

Patient safety will be monitored to ensure that the rate of select AEs described in Section 8.2 (which include: severe fluid overload, untreatable electrolyte abnormalities, severe hyper/hypoglycemia, allergic reactions) does not exceed 25%. If the AE rate exceeds 25%, then the novel treatment approach of (SC + EMR) exceeds an acceptable rate and the trial will suspend accrual, while at the same time, protecting patients from the burden of being exposed to an untoward therapy.

We will employ Bayesian stopping boundaries derived using a beta-binomial distribution. We will consider the treatment as acceptable if the AE rate during the first seven days post administration of (SC + EMR) is below 25%. The following prior probability for the AE rate will be modeled with a beta distribution (1, 1). Allowing θ_T to denote the true rate of AEs, the trial will suspend accrual if the $\text{Prob}(\theta_T > 0.25 | \text{data}) > 0.80$. Patients will be monitored in cohorts of size 10 according to the following stopping boundaries displayed in Table 3.

Table 4 illustrates the operating characteristics associated with the Bayesian stopping rule. The probability of stopping accrual early is 61% if the true AE rate is 30%.

Table 3. Stopping Boundaries assuming prior $\theta_T \sim \text{beta}(1, 1)$

Number of Patients Evaluated	Recommended stopping accrual if \geq AEs are observed
10	4-10
20	7-20
30	10-30
40	13-40
50	15-50

*stopping boundaries and operating characteristics supplied using

<https://ibl.mdanderson.org/BTM/>

Table 4: Operating Characteristics for the Bayesian Sequential Design

True AE Rate	Probability of Stopping Accrual Early	Average Sample Size
0.1	0.014	49.5
0.2	0.180	43.7
0.3	0.610	29.9
0.4	0.928	17.7
0.5	0.996	12.3

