8.3 Adverse Events and Serious Adverse Events

- **An adverse event (AE)** is generally defined as any unfavorable and unintended diagnosis, symptom, sign (including an abnormal laboratory finding), syndrome or disease which either occurs during the study, having been absent at baseline, or if present at baseline, appears to worsen. Adverse events have to be recorded regardless of their relationship to the study intervention.

- **A serious adverse event (SAE)** is generally defined as any untoward medical occurrence that results in death or that is life threatening, requires inpatient hospitalization or prolongation of existing hospitalization, results in persistent or significant disability/incapacity, or in a congenital anomaly.

As discussed in 8.1, the study solution is not a novel pharmaceutical product and is unlikely to cause any significant adverse event. Theoretical complications of the solution are common problems in critical care units. Vigilance and close monitoring, together with high staffing levels in ICU reduce the potential for harm. Bearing these facts in mind, there are only three scenarios, which will be reported as serious adverse events in the EMR group:

- 1) **Anaphylaxis (to study components)**
- 2) **Arrhythmia secondary to electrolyte disturbance**
- 3) **Hypoglycemia (<70mg/dL)**

These will be monitored for via electronic medical records. All suspected adverse reactions and above adverse events must be reported by unit staff or research team to the principle investigator who will provide within 1 week such reports to the Institutional Review Board. We estimate that adverse reactions are not very likely, as this study lacks novel pharmaceutical agents. Patient safety has been thoroughly considered by the study chairs.

Only the adverse events and serious adverse events that happen within the 7 days of enrollment will be logged and reported to the IRB.

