10.3 Interim Analysis

The parameters indicated in the full analysis set comprised of 112 patient for detecting an effect size of -30% (.70 vs .40) with a 2-sided test and Type I error of 5% conferring > 90% power were used to develop interim stopping boundaries based on the method of Lan-DeMets with an O'Brien Flemming type spending function. An interim analysis will be conducted when the first 56 patients (28 patients randomized per treatment arm) have been evaluated for the primary endpoint. Figure 1 provides the stopping boundaries for early termination on a p-value scale for both superiority and futility (East Version 6.3.1). At the interim analysis, a p-value < 0.003 or a p-value > 0.864 elicits early stopping for superiority or futility, respectively. The PI will make the final determination whether to terminate or continue with the trial after evaluating the study results. Accrual will not be suspended while this analysis is being conducted.

Figure 1. Stopping boundaries (on a P-value scale) for early termination due to superiority or futility

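### The 10-patient safety rule in Section 10.6 cannot respond to deaths without a listed adverse event, leaves early deaths unclassified, and no pre-specified rule looks at mortality before 56 patients are evaluated

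*Combined protocol and SAP*

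**What the plan says.** **Safety rule (Section 10.6).** The aim is put this way: "Patient safety will be monitored to ensure that the rate of select AEs described in Section 8.2" stays within a fixed limit. Only one arm is covered: "Patient safety will be monitored group sequentially for the first 50 patients in (SC + EMR) group". Looks come after every 10 of these patients and use a 7-day window. The events are four types ("which include: severe fluid overload, untreatable electrolyte abnormalities, severe hyper/hypoglycemia, allergic reactions) does not exceed 25", in percent). With a beta(1,1) prior, accrual is suspended when the posterior probability that the event rate exceeds 0.25 is above 0.80. This gives boundaries of 4/10, 7/20, 10/30, 13/40 and 15/50.

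**Serious adverse events (Section 8.3).** The general definition includes death, but the section then says "there are only three scenarios, which will be reported as serious adverse events in the EMR group": anaphylaxis, arrhythmia from electrolyte disturbance, and hypoglycemia.

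**Patients who leave early (Section 6.4).** Those who die are followed up with the intervention stopped. Those who withdraw or move to comfort care are removed from the study. Neither 6.4 nor 10.6 says how any of them enter the safety count.

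**Mortality (Section 10.3).** "An interim analysis will be conducted when the first 56 patients (28 patients randomized per treatment arm) have been evaluated for the primary endpoint". Boundaries are named for superiority (p < 0.003) and futility (p > 0.864), and accrual continues meanwhile.

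**Other review.** The PI reviews each patient's data on an ongoing basis (10.4). The DSMB receives adverse event and annual reports (11.4.2) and may review progress as often as it wishes (11.4.4). No threshold for deaths is attached to either.

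**The concern.** The rule in 10.6 is meant to protect patients from a harmful treatment while the trial accrues. Control mortality is expected to be 70% at 28 days (Section 10.2), so some deaths inside the 7-day window are to be expected. A single-arm count of four event types does not register a death that occurs without one of them.

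Two things follow. First, excess early mortality on EMR that does not pass through a listed event could build up without touching the only scheduled rule that operates before the interim. Second, the printed operating characteristics treat every patient as a complete 7-day observation. With early deaths and removals unclassified, the reader cannot tell what rate is being compared with 25%.

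**Working it through.** **1. The plan's own figures.** The smallest x with P(θ > 0.25 | Beta(1+x, 1+n−x)) > 0.80 is 4, 7, 10, 13 and 15 at n = 10 to 50, with posterior probabilities 0.885, 0.870, 0.872, 0.878 and 0.815. An exact binomial recursion over the looks gives early-stop probabilities of 0.014, 0.180, 0.610, 0.928 and 0.996 and average sizes of 49.5, 43.7, 29.9, 17.7 and 12.3 at true rates of 10% to 50%. All match the printed tables, where a stop at the look at 50 is not counted as early. Counting it, the 30% row becomes 0.688. The arithmetic of the rule is sound; the question is what it counts.

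**2. Deaths without a listed event.** Suppose the first ten EMR patients all died with no listed event and were kept as non-events. The posterior is Beta(1, 11), and P(θ > 0.25) = 0.75^11 = 0.042, against a trigger of 0.80.

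**3. Size if early deaths are kept as non-events.** Assumptions: constant, independent hazards; a 35% 7-day event risk in patients under observation; 7-day mortality q of 20%, 30% or 40%. The documents give neither figure. Per 7-day window, λa = −ln(0.65) = 0.4308 and λd = −ln(1−q). The counted rate is λa/(λa+λd) × [1 − 0.65(1−q)].

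| q | λd | Counted rate | Suspension, five looks |
|---|---|---|---|
| 0 | 0 | 35% | 88% |
| 20% | 0.2231 | 0.6588 × 0.480 = 31.6% | 76% |
| 30% | 0.3567 | 0.5470 × 0.545 = 29.8% | 68% |
| 40% | 0.5108 | 0.4575 × 0.610 = 27.9% | 58% |

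**4. Whether the interim fills the gap.** With 28 per arm, control mortality 70% and a two-sided chi-square test, exact enumeration gives the chance of p < 0.003 in the harmful direction as about 1%, 4% and 12% at assumed EMR mortality of 80%, 85% and 90%.

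**5. Adding death to the four events does not work.** With a 20% event rate in survivors and 20% 7-day mortality, the combined rate is 0.20 + 0.20 × 0.80 = 36%. The printed boundaries would then stop accrual early with probability 84%. A mortality rule needs the concurrent control arm.

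**6. A two-arm rule.** At 10, 20, 30, 40 and 50 per arm, suspend if Pr(7-day death EMR > SC | data) > 0.975, with independent beta(1,1) priors. An exact recursion for SC 7-day mortality of 20%, 30% and 40% gives these ranges:

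| True excess on EMR | Suspended by 20 per arm | Suspended by 50 per arm |
|---|---|---|
| None | 3-4% | 6-7% |
| 20 points | 25-30% | 62-67% |
| 30 points | 49-53% | 90-92% |

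**The case against.** A reader might infer that the plan scores an early death as free of adverse events, so that early fatal harm lowers the monitored rate. The documents do not support this. Section 10.6 speaks of patients evaluated and is silent on deaths before day 7. If such patients are treated as not evaluable, the rate is not lowered. Fatal harm that passes through a listed event, such as severe hypoglycemia or an allergic reaction, is counted, and the four types cover the harm routes named in Section 8.1. The figures in step 3 are therefore conditional on one reading.

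The share of treated patients who actually have a listed event within seven days is also a legitimate quantity to monitor. Calling it diluted presumes interest in the risk patients would face if none died early. That objection stands, and it is why the classification must be stated.

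A reader might also infer that nobody can see deaths before the interim. That goes too far. The trial is unblinded, the general definition of a serious adverse event includes death, suspected adverse reactions go to the PI and then to the IRB within a week, and the DSMB may look when it chooses. What is missing is a schedule and a threshold for deaths by arm.

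Finally, the two-arm rule is weak early on. By 20 per arm it misses most 20-point excesses and about half of 30-point excesses.

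**Conclusion.** The point holds as a gap in safety monitoring that should be closed. Under either classification, a death without a listed event cannot raise the 10.6 rate, and the first pre-specified mortality comparison comes at 56 evaluated patients with no named boundary for harm. These statements rest on the documents alone.

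The loss of sensitivity in step 3 is an illustration. It depends on keeping early deaths as non-events, on a 35% event risk, on 7-day mortality of 20-40%, and on constant independent hazards. The printed boundaries and operating characteristics are correct for the rule as written.

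**What to change.** Keep the adverse event rule and its boundaries, and amend Section 10.6 in two places.

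- State how patients who die or are removed before day 7 enter the count.
- At the same 10-patient looks, tabulate 7-day deaths in both arms. Suspend accrual for DSMB review if Pr(7-day death EMR > SC | data) > 0.975, with independent beta(1,1) priors. Record day-7 vital status for patients moved to comfort care as well, since Section 6.4 otherwise removes them.

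Replacing early deaths in the cohort count is a tempting repair but should not be used. It keeps patients with an event whatever their follow-up and drops event-free deaths, which biases the rate upward. On the assumptions of step 3, a 35% risk becomes 0.316/(0.316+0.520) = 37.8%, 0.298/(0.298+0.455) = 39.6% and 0.279/(0.279+0.390) = 41.7%. For an acceptable 20% risk, the chance of suspension over five looks rises from 19.5% to 27%, 33% and 41%. Reaching 50 countable patients at a 35% risk would take about 50/0.836 = 60, 50/0.753 = 66 and 50/0.669 = 75 EMR patients, and the arm has 56.

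The cost is a short amendment. Mortality is already collected (Section 7.2) and a DSMB is already in place. The price is a 6-7% chance of an unneeded suspension over five looks if mortality is equal. Because these looks can act only on harm, they do not inflate the efficacy type I error.

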9.0 CRITERIA FOR INTERVENTION DISCONTINUATION

These include:

- Patient's consent withdrawn
- Patient's discharge from the ICU
- Allergy to any of the components of EMR
- Patient requiring renal replacement therapy
- Patient's death
- Patient changed to Comfort Care status
- Patients receiving greater than 70% of their nutritional needs via enteral nutrition
- Unable to undergo placement of CVC for any technical reasons or withdrawal of CVC
- Severe fluid overload or electrolyte abnormality requiring discontinuation (as described in Chapter 7)
- Jehovah's Witness who decides not to accept albumin.
- If patient develops a known contraindication, or an unspecified condition where the clinician thinks the patient should be taken off the protocol, then there should be a discussion and treatment should be weaned according to safety protocol.

In case of discontinuation, please follow weaning procedure detailed in section 6.7.

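### The 10.6 safety stopping rule counts only *untreatable* electrolyte abnormalities and does not list electrolyte-related arrhythmia, so events the protocol treats as serious or infusion-ending can go uncounted

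*Combined protocol and SAP*

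**What the plan says.** Section 10.6 states that "Patient safety will be monitored group sequentially for the first 50 patients in (SC + EMR) group", in cohorts of 10 over the 7 days of treatment. The events it counts, which it takes from Section 8.2, are "severe fluid overload, untreatable electrolyte abnormalities, severe hyper/hypoglycemia, allergic reactions", and their rate is to stay at or below 25%. The prior is beta(1, 1). Accrual is suspended if the posterior probability that the rate exceeds 0.25 is above 0.80. The Table 3 in that section sets boundaries of 4, 7, 10, 13 and 15 events at 10, 20, 30, 40 and 50 patients, and its Table 4 gives the operating characteristics.

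Three other sections bear on what counts:

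- **Section 8.2** gives laboratory cut-offs and management steps for potassium, sodium, magnesium and phosphate. Under item 2e, magnesium above 4 mg/dl means the intervention is stopped, an adverse event is recorded and the patient is managed under the ICU protocol. For glucose the text gives a target range, calls excursions very likely, and refers to an appendix algorithm whose figure is not shown.
- **Section 8.3** allows only three serious adverse events for the EMR arm: anaphylaxis, "Arrhythmia secondary to electrolyte disturbance", and "Hypoglycemia (<70mg/dL").
- **Section 9.0** lists among its reasons for discontinuation "Severe fluid overload or electrolyte abnormality requiring discontinuation". It cites Chapter 7 for the description, although that text stands in Section 8.2.

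**The concern.** A Bayesian boundary protects patients only against the events fed into it. Section 10.6 takes its events from 8.2 but attaches to the electrolyte class a qualifier that 8.2 does not use and that no section defines. The nearest operational criterion, in 9.0, asks something else: whether the infusion had to stop, not whether the abnormality could be treated. An abnormality can end the infusion and then respond to treatment. It would meet 9.0 and, on the plain wording, fail 10.6.

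The arrhythmia gap is separate. The protocol singles out electrolyte-related arrhythmia as one of three serious harms of this intervention, yet it appears neither in 8.2 nor in the 10.6 list.

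At stake is whether Table 4 describes a defined rule. Two careful readers could apply the same boundaries to the same patients and reach different counts. The trial is un-blinded (4.0), and ongoing safety monitoring lies with the research coordinator and the principal investigator (10.4).

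**Working it through.** **1. Reproduce the plan's own figures.** Inputs, all from 10.6: prior beta(1, 1), limit 0.25, posterior cut-off 0.80, looks at n = 10, 20, 30, 40, 50.

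Boundary at n: the smallest x with P(Beta(1 + x, 1 + n − x) > 0.25) > 0.80.

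| n | Boundary x | Posterior at x | Posterior at x − 1 |
|---|---|---|---|
| 10 | 4 | 0.885 | 0.713 |
| 20 | 7 | 0.870 | 0.744 |
| 30 | 10 | 0.872 | 0.771 |
| 40 | 13 | 0.878 | 0.794 |
| 50 | 15 | 0.815 | 0.720 |

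These are the plan's boundaries. For the stopping probability, let f_k(x) be the probability of reaching look k with x events and no earlier crossing: f_k(x) = Σ f_(k−1)(y) · Bin(x − y; 10, p), summed over y below the previous boundary b_(k−1). Early stopping is the sum of f_k(x) over x ≥ b_k at looks 1 to 4; a crossing at n = 50 is not early. At true rates of 0.1, 0.2, 0.3, 0.4 and 0.5 this gives 0.014, 0.180, 0.610, 0.928 and 0.996, with average sample sizes 49.5, 43.7, 29.9, 17.7 and 12.3. All match Table 4. At exactly 25%, which is not tabulated, the value is 0.376.

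The arithmetic is therefore sound, and the question is only what counts as an event.

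**2. Set the event definitions side by side.**

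| Event in an EMR patient | Status elsewhere | Counted under 10.6 as written? |
|---|---|---|
| Severe fluid overload, fluid discontinued | 8.2 item 1; 9.0 | Yes |
| Anaphylaxis | 8.2 item 4; SAE in 8.3 | Yes, as an allergic reaction |
| Magnesium above 4 mg/dl, infusion stopped, then corrected | 8.2 item 2e: stop and record | No on the plain wording; it was treatable |
| Electrolyte-related arrhythmia, disturbance corrected | SAE in 8.3 | No; not in the list or in 8.2, and the disturbance was treatable |
| Glucose below 70 mg/dl | SAE in 8.3 | Unclear; depends on what *severe* means |

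The third and fourth rows are the gap. The fifth cannot be settled from the text available.

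**3. Illustrate the size.** The documents give no rates for any of these events, so both the counted rate and the added percentage points are assumptions. Added patients are those not already counted for another reason. Early-stop probability, by the same recursion:

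| Counted rate | +0 | +1 point | +2 points | +5 points |
|---|---|---|---|---|
| 20% | 0.180 | 0.213 | 0.250 | 0.376 |
| 25% | 0.376 | 0.423 | 0.470 | 0.610 |
| 30% | 0.610 | 0.655 | 0.697 | 0.808 |

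**The case against.** **The event classes are in 8.2.** This is correct. A reader might infer that 10.6 counts events 8.2 does not contain, but electrolyte abnormalities and hyper/hypoglycemia are both there, and *severe* is used in 8.2 for fluid overload and hypermagnesemia. What is missing is the electrolyte qualifier.

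**A looser reading of *untreatable* is possible.** It could mean not controllable while EMR continues, which would bring it close to 9.0. A refractory abnormality would count on any reading. So the inference that the electrolyte component can almost never be met is not supported. The point that stands is that the protocol does not say which reading applies, and the plain one excludes corrected events.

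**Glucose severity may be defined.** A reader might infer that no severity level exists. The appendix algorithm is a figure not shown, so that cannot be asserted. The same caution applies to the potassium algorithm. Neither possibility supplies the missing arrhythmia item.

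**Hyperkalemia is a poor example.** It is tempting to picture hyperkalemia ending the infusion, but 8.2 says EMR II continues despite hyperkalemia. The magnesium item is the example the protocol itself supplies.

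**Arrhythmia is not unmonitored.** It goes to the principal investigator and to the IRB within a week (8.3), and the DSMB receives adverse event reports and may review when it wishes (11.4.2, 11.4.4). One numerical rule need not hold every serious event. This lowers the stakes, but those channels do not feed the accrual boundary. The list is introduced by a word that could be read as non-exhaustive, yet it stays tied to 8.2, where arrhythmia is absent.

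**Ambiguity cuts both ways.** If a broad reading made 50% of patients count, early stopping would have probability 0.996, and 8.2 calls glucose excursions very likely. Simply deleting the qualifiers would be no remedy.

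**Conclusion.** The concern holds in a limited form. The 10.6 electrolyte criterion does not match 8.2 or 9.0, and the list omits a serious event that 8.3 names. Followed as written, the rule can leave out a corrected electrolyte abnormality that ended the infusion, and an electrolyte-related arrhythmia.

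How much this weakens the rule cannot be established. A reader might move down Table 4 from 30% to 20% and conclude that the stopping probability falls from 0.61 to 0.18. That presumes 10 percentage points of patients go uncounted, for which the documents offer no basis. It also applies the 25% limit, set for the counted events, to a wider set. The smaller additions shown above are equally assumed; they indicate only that the rule is sensitive near its limit, where 1 to 5 points move the early-stop probability from 0.38 to between 0.42 and 0.61.

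The sponsor should correct this, because the omitted events are ones the protocol itself ranks as serious or infusion-ending and the repair is cheap.

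**What to change.** Reconcile 8.2, 8.3, 9.0 and 10.6 into one definition, counted once per patient within the 7-day window:

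- Replace *untreatable* electrolyte abnormalities with the criterion already in 9.0, an electrolyte abnormality leading to discontinuation of EMR.
- Add electrolyte-related arrhythmia.
- Keep severe fluid overload, allergic reactions, and both hyper- and hypoglycemia. A list built only from the 8.3 events and discontinuations would drop hyperglycemia.
- Have the sponsor state how *severe* glucose events relate to the hypoglycemia SAE in 8.3 and to the appendix algorithm.
- Correct the Chapter 7 cross-reference in 9.0.

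Then confirm that 25% is the intended limit for this event set. If the limit, prior and cut-off are unchanged, the boundaries and Table 4 stand, because they depend only on those values and the looks. A new limit would require both to be recalculated.

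The cost is mainly wording. The 8.3 events are tracked through electronic records and infusion stop times are recorded (6.4); the reason for each stop would need to be logged with them. The downside is that somewhat more events count, so suspension of accrual becomes somewhat more likely. Discontinuation also remains partly a clinical judgement. No dose or clinical management rule needs to change for the count to be defined.
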